evaluation of biopsy tissue by the PAC there is no evidence of HSIL (Subgroups A or B), the subject will continue to Week 96 for vulvoscopy and biopsy of the same lesion as at study start. Investigator If HSIL remains but there is a reduction in lesion size or no increase in lesion size from baseline (Subgroups C or D), the Investigator has the option to give the subject a 6th dose of VGX-3100 at Week 78, and the subject will continue on study with vulvoscopy and biopsy at Week 96. Alternatively, the Investigator may choose to treat the subject with surgical or standard treatment, and the subject will continue on study without further biopsy.

The decision process following results of the Week 74 biopsy are as described in [Figure 4](#) and are as follows: At Week 96, the subject will undergo repeat vulvar punch biopsy/biopsies of the same lesion as study start, but from the region of potentially most advanced disease based upon the judgment of the Investigator. (see [Table 2](#)). If there is no vulvar HSIL (Subgroups A or B), no further procedures are required. If after evaluation of biopsy tissue by the PAC there is vulvar HSIL (Subgroups C or D), or worsening disease (Subgroup E), the subject will receive surgical or other standard treatment.

In the event of worsening disease (i.e., Subgroup E - any increase in lesion area from baseline or worsening to cancer), the subject will receive surgical treatment per the Investigator's judgment and will continue on study through Week 100 with vulvoscopy, but without further study treatment or biopsy. For a finding of carcinoma, subjects will receive surgical treatment, and be discontinued from study treatment. The event will be reported as an SAE per [section 7.1.4](#). If wide excision is required, the sample obtained will be sent to the PAC for evaluation.

Pre-biopsy Vulvoscopy Finding	Minimally required procedure
No acetowhite lesion	Vulvar punch biopsy and lesion photography; biopsy should be conducted of the same qualifying lesion as study entry from the region of potentially most advanced disease based upon judgment of the Investigator.
Acetowhite Lesion	Vulvar punch biopsy and lesion photography; biopsy should be conducted of the same qualifying lesion as study entry from the region of potentially most advanced disease based upon judgment of the Investigator.

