Multiple acetowhite lesions	Vulvar punch biopsies and lesion photography; biopsy should be conducted of the same qualifying lesions as study entry from the region of potentially most advanced disease based upon judgment of the Investigator.

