7. Exploratory Endpoints #2, #3, and #9 have been updated to include the efficacy of four doses as well as more than 4 doses. Clarifying text has been added to Section 8.9 regarding the analysis as it relates to the Week 74 and 96 evaluation according to number of doses received.
8. HLA haplotyping and associated Exploratory Endpoint #6 have been removed from the protocol due to consideration of the results from Inovio's Phase 2 cervical study which showed no clear association of HLA background as a predictor of response. No testing has been performed on HPV-201 subject samples. HLA testing has been removed from all applicable protocol sections and the ICF has been updated to remove this procedure.
9. Section 3.2 and the Protocol Synopsis have been updated to indicate that sites will biopsy all lesions at Weeks 48, 74, and 96 (as applicable). New lesions, and lesions that did not qualify at Screening, should be biopsied post-screening and sent for evaluation. Pathology and genotyping results will be included in the determination of efficacy for the

- primary, secondary, and exploratory endpoints. This has been updated accordingly in Section 8.9 of the protocol.
10. Responder and non-responder definitions for the Secondary/Exploratory endpoints have been provided in Section 3.2.
  11. The Efficacy Assessment (Protocol Synopsis and Section 3.2) has been updated to differentiate between lesion photographs and lesion measurements. Lesion measurements are only done at Screening, Day 0, Week 48, Week 74, and at Week 96 as applicable.
  12. Figure 2 has been updated to align with wording in the protocol indicating that subjects in Subgroup E continue on study with vulvoscopy, but without further study treatment or biopsy, in place of the previous inconsistent wording that subjects in Subgroup E are followed for safety only. All procedures outlined in the schedule of events are conducted on subjects in Subgroup E, except for biopsy or additional study treatment.
  13. The Decision process at Week 52 in the Efficacy Assessment (Protocol Synopsis and Section 3.2) has been updated to include new lesions identified at evaluation. A discussion will take place between the Medical Monitor and the Principal Investigator to determine if additional dosing is appropriate when new HPV-16/18 high-grade vulvar lesions are identified.

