- k Photography of the acetowhite stained qualifying lesion(s) must be performed prior to and after biopsy, and at all vulvoscopy examinations. If a pre-biopsy digital photograph is not available for a historical biopsy sample at screening, a post biopsy photo will be sufficient. Additionally, standardized high resolution digital photographic imaging should be obtained during examinations of the vagina if lesions are identified, for documentation.
- l Tissue specimen from all excised tissue obtained prior to or at the subjects in-person discharge visit must be reviewed by the PAC and will be sent to the central laboratory for HPV testing. All lesions will be biopsied at Week 48, 74, and 96 (as applicable), per Amendment 5.0.
- m HPV genotyping is performed on vulvar tissue specimen using a PCR based assay.
- n Potential dosing, post-treatment assessment, and distribution of the Participant Diary at Week 52 and Week 78 is applicable for partial responders only. Partial responders who reach Week 78 after Amendment 5.0 will not be offered a 6th dose.
- o Subjects will take home imiquimod plus an imiquimod dosing log to document their use of imiquimod. Administration of imiquimod begins on Day 0.
- p A phone call will be used to review the Participant Diary (PD) with subject within 8-14 days following dose 1 and 2. The patient will be expected to bring the PD to the next visit for review.
- q PRO measures (SF-36v2™, EQ-5D-5L, WOMAN-PRO) plus two additional questions will be assessed as described in [Section 6.8](#).

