In the event of worsening disease prior to the end of the study (i.e., Subgroup E), the subject will receive surgical treatment per the Investigator's judgment and will continue on study with vulvoscopy, but without further study treatment or biopsy. In the event of worsening disease at the final visit, the subject will receive standard of care treatment (not part of study activities) per their treating physician. If wide excision is conducted at or prior to the subjects last on site visit, the sample obtained will be sent to the PAC for evaluation. For a finding of carcinoma, subjects will receive surgical treatment, and be discontinued from study treatment. The event will be reported as an SAE per [section 7.1.4](#).

All visible lesions should be biopsied at Week 48. For subjects for whom Week 78 is their final visit, all visible lesions should be biopsied at Week 74. For subjects for whom the final visit is Week 96, all visible lesions should be biopsied at Week 96.

If there is a new lesion identified at evaluation, or a non-qualifying lesion that is rebiopsied and confirmed to be vulvar HSIL and HPV-16/18 positive at evaluation, a discussion will take place between the Medical Monitor and the Principal Investigator to determine if additional dosing at Week 52 is appropriate.

Pre-biopsy Vulvoscopy Finding	Minimally required procedure
No acetowhite lesion	Vulvar punch biopsy and lesion photography; biopsy should be conducted of the same qualifying lesion as study entry from the region of potentially most advanced disease based upon judgment of the Investigator; new lesions or lesions that did not qualify at baseline should be biopsied at evaluation.
Acetowhite Lesion	Vulvar punch biopsy and lesion photography; biopsy should be conducted of the same qualifying lesion as study entry from the region of potentially most advanced disease based upon judgment of the Investigator; new lesions or lesions that did not qualify at baseline should be biopsied at evaluation
Multiple acetowhite lesions	Vulvar punch biopsies and lesion photography; biopsy should be conducted of the same qualifying lesions as study entry from the region of potentially most advanced disease based upon judgment of the Investigator; new lesions or lesions that did not qualify at baseline should be biopsied at evaluation

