### 3.2.1 DEFINITION OF RESPONDER AND NON-RESPONDER FOR THE PRIMARY ENDPOINT

A treatment responder is defined as a subject with no histologic evidence of vulvar HSIL and no evidence of HPV-16 or HPV-18 in vulvar tissue at evaluation and who did not receive any non-study related treatment for vulvar HSIL. A treatment non-responder is a subject with histologic evidence of vulvar HSIL or vulvar carcinoma at evaluation, or a subject with evidence of HPV-16/18 at evaluation, or a subject who received non-study related treatment for vulvar HSIL. Any case of histologically confirmed progression to carcinoma according to the PAC is considered a non-responder.

Responder and non-responder definitions ([Table 3](#)) take into account both histopathologic regression of vulvar HSIL and virologic (HPV-16/18) clearance from tissue samples since HPV persistence is an important factor in the clinical progression of HSIL.

Table 3: Definition of Responder and Non-responder for the Primary Endpoint	
Responder	Non-Responder
Subject with no histologic evidence of vulvar HSIL AND Subject with no evidence of HPV-16 or HPV-18 in vulvar tissue at evaluation AND Subject who did not receive any non-study related treatment for vulvar HSIL	Subject with histologic evidence of vulvar HSIL or vulvar carcinoma at evaluation OR Subject with evidence of HPV-16 or HPV-18 in vulvar tissue at evaluation OR Subject who received non-study related treatment for vulvar HSIL

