## 8.9 EFFICACY ANALYSIS

The true treatment effect on the primary endpoint is  $p$ , where  $p$  denotes the true population probability of the primary endpoint for each arm. The primary hypothesis of superiority is:

$H_0: p \leq 0.02$  vs.  $H_1: p > 0.02$ , for each treatment study group separately.

A p-value for these hypothesis tests and corresponding 95% confidence intervals will be computed based on the exact method of Clopper-Pearson. Superiority will be concluded if the one-sided p-value is  $< 0.025$  and the corresponding lower bound of the 95% CI exceeds 0.02.

The secondary efficacy binary endpoints will be analyzed in the same manner as the primary hypothesis, but without the hypothesis test p-values. All of the efficacy binary endpoints will be analyzed in two ways: a) based on qualifying and new lesions, and b) based on all lesions. Also, the Week 74 binary endpoint will be analyzed overall, and according to four or five doses received, and the Week 96 binary endpoint will be analyzed overall, and according to four, five, or six doses received.

For the analyses, the efficacy time frame is defined by any time starting from 14 days prior to the -specified visit week.

The anatomic extent endpoint will be analyzed by calculating the mean percent change and associated 95% t-distribution based confidence interval. The percentage of subjects with no clinically significant lesion resolution (reduction in lesion size of 25% or less), partial lesion resolution (26-99% reduction), and complete reduction (100% reduction) will be summarized with point estimates and associated exact Clopper-Pearson 95% confidence intervals.

An exploratory analysis will examine clearance outside of the vulva. This will be analyzed in the same manner as vulvar clearance.

An exploratory analysis will examine the relationship between the primary efficacy endpoint and a) miRNA results, b) vulvoscopy results, and c) HPV results. Relationships will be examined with contingency tables and/or logistic regression models which model the primary endpoint versus these results and treatment group as regressor variables.

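### Section 8.9 pools women biopsied under two lesion rules and leaves out the one lesion set required under both, the qualifying lesions

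*Protocol*

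**What the plan says.** **Version 3.0.** Section 3.2 and its table of minimum biopsy procedures (Table 2) send the response biopsy to lesions identified at entry. For a single lesion, "biopsy should be conducted of the same qualifying lesion as study entry"; for several, "biopsy should be conducted of the same qualifying lesions as study entry". A qualifying lesion is one found at screening to be HPV-16/18 positive, with HSIL confirmed by the Pathology Adjudication Committee (PAC).

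**Version 5.0 (19 December 2019).** Section 3.2 now says "All visible lesions should be biopsied at Week 48". Each row of Table 2 adds that "new lesions or lesions that did not qualify at baseline should be biopsied at evaluation", and a footnote to the Schedule of Events says "All lesions will be biopsied at Week 48, 74, and 96 (as applicable), per Amendment 5.0". The Summary of Changes says of the added tissue that "Pathology and genotyping results will be included in the determination of efficacy", and it names the primary, secondary and exploratory endpoints.

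**Response definition.** Section 3.2.1 keeps the same responder rule in both versions: "A treatment non-responder is a subject with histologic evidence of vulvar HSIL or vulvar carcinoma at evaluation". Evidence of HPV-16/18 in vulvar tissue has the same effect.

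**Analysis.** Section 8.9 (version 5.0) fixes two lesion sets for every binary efficacy endpoint: "All of the efficacy binary endpoints will be analyzed in two ways: a) based on qualifying and new lesions, and b) based on all lesions". It has no analysis on qualifying lesions alone, no split by the biopsy rule in force, and no rule for a visible lesion that was not sampled. Section 8.13 imputes nothing.

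**The concern.** Both lesion sets in section 8.9 need tissue that version 3.0 did not require. A woman seen at Week 48 under version 3.0, whose qualifying lesion had cleared but who had a further unsampled lesion, is a responder on the tissue available. The same woman seen under version 5.0 would have that lesion biopsied and could be a non-responder. The two analyses therefore combine incomplete and complete ascertainment under one label.

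The primary endpoint is tested against a fixed 2% benchmark with about 21 evaluable women in one arm and 10 in the other. A few women classified on less tissue could matter. The Week 74 endpoints have the same problem: a woman sampled under the old rule at Week 48 and the new rule at Week 74 can change status through sampling alone.

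**Working it through.** **1. Women assessed under the old rule exist.** Version 5.0 makes provision for women already beyond Week 78, who passed Week 48 at least 78 − 48 = 30 weeks earlier. By date, 48 weeks (336 days) before 19 December 2019 is 17 January 2019. A woman dosed first on or before that day was due at Week 48 before version 5.0 was issued. The cut-off is later where site IRB approval came later. Accrual dates are not given, so the number of such women is unknown.

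**2. Direction.** Under an any-positive-is-failure rule, adding tissue from further lesions can turn a responder into a non-responder but never the reverse. If q is the share of qualifying-lesion responders who would fail on a further lesion, then

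rate on all lesions = (rate on qualifying lesions) × (1 − q), with q ≥ 0.

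At q = 0 there is no effect.

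**3. The plan's own power figure.** Inputs from section 8.3: 36 women randomized 2:1, 90% evaluable, 20% and 28% against 2%, one-sided 0.025, 80% power. Exact binomial:

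- VGX-3100 alone, n = 21 (21/0.9 = 23.3, rounded up to 24): success needs 3 responders. P(X ≥ 3 | 21, 0.02) = 0.0081; power at 20% is 82.1%.
- Combination, n = 10 (10/0.9 = 11.1, rounded up to 12): success needs 2 responders. P(X ≥ 2 | 10, 0.02) = 0.0162; power at 28% is 81.7%.

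The stated 80% is reproduced as at least 80%, and 24 + 12 = 36.

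**4. Sensitivity to one woman.** With 21 evaluable, 3 responders give p = 0.008 and 2 give p = 0.065. With 10 evaluable, 2 give p = 0.016 and 1 gives 1 − 0.98^10 = 0.18.

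**5. Illustrative size.** The documents give no value of q; those below are assumptions. Take 20% as the qualifying-lesion rate and n = 21. The half-and-half column has 10 women under the old rule and 11 under the new.

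| q | all-lesion rate | power, all old rule | power, half and half | power, all new rule |
|---|---|---|---|---|
| 0.1 | 18% | 82.1% | 78.9% | 75.6% |
| 0.2 | 16% | 82.1% | 75.3% | 67.6% |
| 0.3 | 14% | 82.1% | 71.3% | 58.0% |
| 0.5 | 10% | 82.1% | 62.0% | 35.2% |

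The same treatment effect thus has a different chance of success depending only on the mix of rules.

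**6. Type I error.** Suppose instead that 2% is an all-lesion benchmark and, at the extreme, every woman was assessed under the old rule. The effective null is 2%/(1 − q):

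| q | effective null | P(≥3 of 21) | P(≥2 of 10) |
|---|---|---|---|
| 0 | 2.0% | 0.008 | 0.016 |
| 0.1 | 2.2% | 0.011 | 0.020 |
| 0.2 | 2.5% | 0.015 | 0.025 |
| 0.3 | 2.9% | 0.021 | 0.032 |
| 0.5 | 4.0% | 0.050 | 0.058 |

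In the larger arm the error stays below 0.025 up to q = 0.3. In the smaller arm it passes 0.025 just above q = 0.2 (0.0246 at q = 0.2).

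**The case against.** Several points against the concern have force.

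- **A reader might infer that women assessed early could not fail on other lesions.** The documents do not support that. Table 2 is a minimum. Version 3.0 sections 6.12 and 6.14 take tissue from two lesions in multifocal disease, chosen as potentially the most advanced. Wide excision at Week 48 is at the Investigator's discretion, unscheduled biopsies are allowed, and biopsy samples go to the PAC. Non-study treatment for vulvar HSIL also counts as failure. The gap is confined to women who had a further lesion that was not sampled.
- **A reader might infer that response must fall from Week 48 to Week 74.** Only the sampling component runs one way. Later regression or a fifth dose can raise response. Section 8.9 plans no Week 48 to Week 74 change; Week 74 is a separate exploratory proportion.
- **A reader might infer a biased comparison between arms, since the imiquimod group stopped enrolling first.** Section 8.9 tests each arm separately against 2% and plans no between-arm efficacy test. Treatment group appears only as a regressor in exploratory models. The mix of rules by arm is unknown without accrual dates.
- **One woman can decide any exact test of this size.** True. Step 4 measures how little bias is needed; it is not evidence that bias occurred.
- **The statistical analysis plan could settle this, and section 8.4 limits the modified intention-to-treat set to women who have the endpoint.** A plan not shown may add a split by version. But the protocol itself fixes the two lesion sets, and section 8.4 does not tie having the endpoint to how completely lesions were sampled.

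These points limit the claim. They leave unanswered that neither planned lesion set was required to be sampled in all women.

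**Conclusion.** The concern holds as an ascertainment bias of known direction and unknown size in the primary endpoint and the other binary efficacy endpoints. For women assessed before Amendment 5.0, the rates on qualifying-and-new lesions and on all lesions can only be equal to or higher than under the new rule. The common lesion set that would remove the problem is not analysed.

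The size depends on two unstated quantities: how many Week 48 and Week 74 visits fell under the old rule, and how often an unsampled lesion was positive. The ranges above are illustrations. They include no effect at all, and for moderate q they do not overturn type I error control in the larger arm. This does not invalidate the trial. It should be fixed before analysis because the margin for success is a single responder and the remedy is cheap.

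A related inconsistency adds to it. Version 5.0 sections 6.11 and 6.13 still direct biopsy of two lesions in multifocal disease, while section 3.2 and the Schedule of Events footnote call for all lesions. Sampling under version 5.0 may therefore also have varied between women.

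**What to change.** In section 8.9:

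1. Add an analysis of each Week 48 and Week 74 binary endpoint on qualifying lesions only, as the common set across versions. Base any Week 48 versus Week 74 comparison on it.
2. Report the qualifying-and-new and all-lesions analyses by the biopsy rule in force at the visit: before or under Amendment 5.0.
3. As a sensitivity analysis only, and where the vulvoscopy record allows, repeat those two analyses with women who had a visible unbiopsied lesion excluded and, separately, counted as non-responders. This should not be the main analysis: section 3.2 bases efficacy on histopathology, and the responder tables do not make an unbiopsied acetowhite area a failure.

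Separately, reconcile version 5.0 sections 6.11 and 6.13 with section 3.2 and the Schedule of Events footnote on how many lesions are biopsied in multifocal disease.

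The cost is analysis wording and a few tables. Items 1 and 2 need only biopsy results by lesion and visit dates against the date each site adopted the amendment. Item 3 may be incomplete, because version 3.0 lists Week 48 photography for qualifying lesions and does not say that every further lesion was recorded and matched to a biopsy.

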## **6.11 VULVAR HPV TESTING**

At Screening, Weeks 48, 74, and 96, a vulvar punch biopsy sample of approximately 4 mm will be obtained and sent to a central laboratory for HPV genotyping by PCR. Samples will not be obtained at week 96 on subjects who complete the study prior to that timepoint per Amendment 5.0.

In the case of multifocal disease, a vulvar biopsy of approximately 4 mm will be obtained from two lesions that potentially contain the most advanced disease as judged by the Investigator. The subject will be requested to abstain from sexual activity and refrain from use of douching to eliminate potential interference with the results of HPV testing.

The subject will be requested to abstain from sexual activity and refrain from use of douching or vaginal lubricants/medication for a period of 24 hours prior to collection of vulvar punch biopsy to eliminate potential interference with the results of HPV testing.

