### 6.13 VULVOSCOPY, PHOTOGRAPHS, AND BIOPSIES

Eligible subjects are enrolled in the study based on the diagnosis of vulvar HSIL confirmed by the PAC. Subjects will undergo vulvoscopy to identify the lesion(s). Interval vulvoscopies will be performed at Day 0, Weeks 4, 12, 27, 48, 74, and at Week 96 for subjects completing Week 96 prior to or under Amendment 5.0. Vulvoscopic visualization of a normal appearing vulva is insufficient evidence to confirm disease regression. An additional visit may be scheduled to perform vulvoscopy if worsening of disease is suspected.

Digital photographs of the vulva will be captured after application of acetic acid to document the clinical findings. If a biopsy or surgical excision is performed, images of the vulva should be collected before and after the procedure. Each site will be instructed on 1) the technique for capturing the proper images using a standard approach, and 2) the process for uploading the images to a secure server.

In the case of multifocal disease, the two lesions that potentially contain the most advanced disease as judged by the Investigator and which is of adequate size to ensure that a visible lesion remains after punch biopsy should be chosen for vulvar biopsy and documented using photography.

Biopsies should not be performed at any visit other than at entry (screening), Week 48, Week 74, or at Week 96 for subjects completing these timepoints prior to or under Amendment 5.0, unless the PI suspects disease progression. All biopsy samples obtained prior to or at the final discharge visit must be sent to the PAC for review. Investigator guidelines for managing the findings of unscheduled biopsies for suspected disease progression are described in [Table 12](#). Consult the Medical Monitor for any planned departures from these guidelines.

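### Section 8.9 analyses the primary endpoint on two lesion sets without saying which one decides superiority, and one of the sets departs from Table 3

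*Protocol*

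**What the plan says.** All references are to Protocol Version 5.0 unless stated.

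- **Analysis.** Section 8.1 describes the primary endpoint as binary. Section 8.9 then says that every binary efficacy endpoint "will be analyzed in two ways: a) based on qualifying and new lesions, and b) based on all lesions". The superiority rule in the same section requires a one-sided p-value below 0.025 and that the "corresponding lower bound of the 95% CI exceeds 0.02", for each treatment group separately. It names no lesion set.
- **Endpoint definition.** Table 3 in section 3.2.1 works at subject level. HSIL or carcinoma at evaluation makes a non-responder, and so does "Subject with evidence of HPV-16 or HPV-18 in vulvar tissue at evaluation" or non-study treatment for vulvar HSIL. Nothing limits this to particular lesions.
- **Qualifying lesion.** Section 3.2 requires both HPV-16/18 positivity and HSIL confirmed by the adjudication committee at screening. Section 3 says two lesions should be chosen for screening biopsy in multifocal disease, while the stratum in section 8.2 is two or more lesions.
- **Sampling at evaluation.** Section 3.2 says "All visible lesions should be biopsied at Week 48". The synopsis agrees, and a Table 1 footnote says "All lesions will be biopsied at Week 48, 74, and 96 (as applicable), per Amendment 5.0". Section 6.11, which opens by listing Screening and Weeks 48, 74 and 96, says that in multifocal disease "a vulvar biopsy of approximately 4 mm will be obtained from two lesions that potentially contain the most advanced disease". Section 6.13 carries similar wording, "In the case of multifocal disease, the two lesions that potentially contain the most advanced disease as judged by the Investigator", with no visit named.

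**The concern.** Two analyses of the primary endpoint are prescribed on an equal footing, and there is one verdict to reach. If they disagree, the protocol does not say which one answers the primary hypothesis. The sets are also not interchangeable. Set (a) disregards any lesion that was there at screening but did not meet the qualifying definition, whereas Table 3 counts disease wherever it is found.

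This is not a remote case. Section 3.2 itself provides for a non-qualifying lesion that proves, at evaluation, to be HSIL and HPV-16/18 positive. In an open-label trial with few expected responders, leaving the deciding definition unsettled allows it to be chosen once the results are known. Multifocal disease is where the two sets are most likely to part.

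**Working it through.** **1. The plan's own sample size.** Inputs from sections 8.3 and 8.9: null rate 0.02; alternatives 0.20 (VGX-3100 alone) and 0.28 (with imiquimod); one-sided 0.025; 80% power; 90% evaluable; 2:1 allocation of 36. Method: exact binomial, where r is the smallest count with P(X ≥ r | n, 0.02) < 0.025 and power is P(X ≥ r | n, p1).

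- At 0.20: n = 20 gives power 0.794; n = 21 gives r = 3 and power 0.821. 21/0.9 = 23.3, so 24.
- At 0.28: n = 9 gives power 0.766; n = 10 gives r = 2 and power 0.817. 10/0.9 = 11.1, so 12.
- Total 24 + 12 = 36. The plan's figure is reproduced and is not in dispute.

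**2. The cut-offs.** Evaluable numbers: 0.9 × 24 = 21.6, about 22; 0.9 × 12 = 10.8, about 11.

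| Evaluable | Responders | One-sided exact p | Clopper-Pearson 95% lower bound | Superior? |
|---|---|---|---|---|
| 22 | 3 | 0.0093 | 0.029 | yes |
| 22 | 2 | 0.071 | 0.011 | no |
| 11 | 2 | 0.0195 | 0.023 | yes |
| 11 | 1 | 0.199 | 0.002 | no |

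One subject moves the observed rate by 1/22 = 4.5 points or 1/11 = 9.1 points. Expected responders at the design rates are 22 × 0.20 = 4.4 and 11 × 0.28 = 3.1, so the cut-offs lie close to the planned result.

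**3. The two sets compared.** Take a woman with one lesion that qualified and has cleared, and a second that was present at screening, did not qualify, and shows HSIL with HPV-16/18 at Week 48. Assume no non-study treatment.

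- Set (a): the second lesion is not considered, so she is a responder.
- Set (b): it is considered, so she is a non-responder.
- Table 3: HSIL and HPV-16/18 are present in vulvar tissue, so she is a non-responder.

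Set (b) contains every lesion in (a). Anyone clear on (b) is clear on (a), but not conversely. Responders under (b) are therefore a subset of those under (a), and the rate under (a) is equal or higher.

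**4. Type 1 error.** Because of that nesting, declaring success if either set passes is the same as testing (a) alone. The exact level at n = 22 with r = 3 and a true rate of 0.02 under (a) remains 0.0093.

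**5. Size if the rates differ.** The documents give no rate by lesion set. As an assumption, let 0.20 hold under (a) and a lower rate under (b). Power at n = 22 is 0.85 at 0.20, 0.75 at 0.17, 0.66 at 0.15 and 0.50 at 0.12.

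**The case against.** The strongest reply is that the protocol already defines the primary endpoint. Table 3 sits in a section headed for that endpoint, carries no lesion restriction and matches set (b). The Version 5.0 summary of changes also says results from new and non-qualifying lesions count towards the primary endpoint. On that view (a) is merely an added analysis, and a separate SAP, not available here, could label it so. This stands as an argument for which set should decide. It does not remove the problem, because section 8.9 puts both sets on the same footing for the primary, and (a) applied as written contradicts Table 3.

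Other points on that side also stand. Both analyses must be reported, so neither can be quietly dropped. Histology is read masked by two pathologists (section 10.4.2). The reversal needs a result exactly at the cut-off: at a true rate of 0.20, the chance of exactly 3 of 22 is 1540 × 0.20³ × 0.80¹⁹ = 0.18. One of those responders must also have residual disease confined to a non-qualifying lesion, and the documents give no frequency for that. The figures for 11 subjects use the planned imiquimod group, whose enrolment Version 3.0 halted.

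Several stronger readings are tempting and are not supported:

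- *Two p-values per group inflate type 1 error.* They do not, because the sets are nested.
- *Women seen at Week 48 before Amendment 5.0 had only qualifying lesions sampled.* Version 3.0 Table 2 set a minimum, and its section 6.12 called for two lesions judged most advanced, without limiting these to qualifying ones.
- *Unsampled lesions are counted as disease-free.* No section says so; the protocol gives no rule for a visible lesion left unbiopsied.
- *A third lesion can never qualify.* Two are to be chosen at screening, but section 6.1.1 also accepts blocks from a previous biopsy without stating a number.
- *Section 6.13 plainly contradicts section 3.2.* Its condition that visible lesion remain after biopsy resembles the screening criterion. The clear conflict is section 6.11.

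**Conclusion.** The concern holds in a limited form. Section 8.9 leaves open which lesion set decides the primary hypothesis, and set (a) conflicts with Table 3 for any woman whose only residual HSIL or HPV-16/18 is in a lesion present at screening that did not qualify. The harm is an undefined and possibly laxer primary endpoint in an open-label trial, not an inflated error rate. Its size is one subject at the cut-off: 3 against 2 of 22, or 2 against 1 of 11. This assumes the planned group sizes with 90% evaluable. How often the two sets will disagree cannot be estimated from the protocol.

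Two related matters remain. The all-lesion biopsy rule came with Amendment 5.0, so women biopsied at Week 48 earlier may contribute fewer lesions to set (b); how many is not stated. And the current text gives sites two different sampling instructions for multifocal disease.

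**What to change.** 1. In section 8.9, state that the superiority test uses the Table 3 definition over all sampled vulvar tissue, set (b), and that set (a) is a sensitivity analysis. Settle this before Week 48 results by lesion set are examined.
2. Add a supportive table of the primary result by whether the Week 48 biopsy was done before or after Amendment 5.0.
3. Reconcile the biopsy instructions: section 6.11, and the wording in section 6.13 that names no visit, against section 3.2, the synopsis and the Table 1 footnote. Which sampling rule stands is for the sponsor and investigators to decide.

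The cost is a sentence in section 8.9, aligned wording elsewhere and one extra table, since the set (a) analysis is already planned. Sample size, alpha and treatment do not change. The headline response rate may be lower than under (a).
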